7.1.3.1 Assessment Guidelines

Please note the following:

- The same diagnostic method, including use of contrast when applicable, must be used throughout the study to evaluate a lesion.
- All measurements should be taken and recorded in millimeters (mm), using a ruler or calipers.

- Ultrasound is not a suitable modality of disease assessment. If new lesions are identified by ultrasound, confirmation by CT or MRI is required.
- FDG-PET is generally not suitable for ongoing assessments of disease. However FDG-PET can be useful in confirming new sites of disease where a positive FDG-PET scan correlates with the new site of disease present on CT/MRI or when a baseline FDG-PET was previously negative for the site of the new lesion. FDG-PET may also be used in lieu of a standard bone scan providing coverage allows interrogation of all likely sites of bone disease and FDG-PET is performed at all assessments.
- If PET/CT is performed then the CT component can only be used for standard response assessments if performed to diagnostic quality, which includes the required anatomical coverage and prescribed use of contrast. The method of assessment should be noted as CT on the electronic CRF.
- CT and MRI: Contrast enhanced CT with 5mm contiguous slices is recommended.

Minimum size of a measurable baseline lesion should be twice the slice thickness, with a minimum lesion size of 10 mm when the slice thickness is 5 mm. MRI is acceptable, but when used, the technical specification of the scanning sequences should be optimized for the evaluation of the type and site of disease and lesions must be measured in the same anatomic plane by use of the same imaging examinations. Whenever possible, the same scanner should be used.

X-ray: Should not be used for target lesion measurements owing to poor lesion definition.

Lesions on chest X-ray may be considered measurable if they are clearly defined and surrounded by aerated lung; however chest CT is preferred over chest X-ray.

Brain Scan: If brain scans are required, then contrast enhanced MRI is preferable to contrast enhanced CT.

7.1.3.2 Measurable and Non-measurable Definitions

A measurable lesion is a non-nodal lesion that can be accurately measured in at least one dimension (longest dimension) of:

- ≥ 10 mm with MRI or CT when the scan slice thickness is no greater than 5mm. If the slice thickness is greater than 5mm, the minimum size of a measurable lesion must be at least double the slice thickness (e.g., if the slice thickness is 10 mm, a measurable lesion must be ≥ 20 mm).
- ≥ 10 mm caliper/ruler measurement by clinical exam or medical photography.
- ≥ 20 mm by chest x-ray.

Additionally, lymph nodes can be considered pathologically enlarged and measurable if:

Protocol date: August 30, 2016

Confidential

- ≥ 15 mm in the short axis when assessed by CT or MRI (slice thickness recommended to be no more than 5 mm). At baseline and follow-up, only the short axis will be measured.

A non-measurable lesion is:

- All other lesions including lesions too small to be considered measurable (longest diameter < 10 mm or pathological lymph nodes with ≥ 10 mm and < 15 mm short axis) as well as truly non-measurable lesions, which include: ascites, pleural or pericardial effusions, inflammatory breast disease, lymphangitic involvement of the skin or lung, abdominal masses/abdominal organomegaly identified by physical exam that is not measurable by reproducible imaging techniques (Eisenhauer 2009).

Measurable disease: The presence of at least one measurable lesion. Palpable lesions that are not measurable by radiologic or photographic evaluations may not be utilized as the only measurable lesion.

Non-Measurable only disease: The presence of only non-measurable lesions. Note: nonmeasurable only disease is not allowed per protocol.

7.1.3.3 Response Criteria (irRC)

7.1.3.3.1 Immune-related RECIST Criteria (irRECIST) Overview

- All measurements are undimensional
- If a patient is classified as having progressive disease, confirmation by a second scan at least 4 weeks later in the absence of rapid clinical deterioration is required to assess for a late response.
- The presence of new lesions does not constitute disease progression by itself.
- Target lesions and new lesions are incorporated into overall tumor burden which is used to evaluate progression or responses as in the following:

Tumor Burden = Sum of the Diameter (target) + Sum of the Diameter (new)

7.1.3.3.2 Target Lesions

- Up to 5 lesions may be selected as target lesions (up to 2 per organ).
- Immune-related Complete Response (irCR): Disappearance of all target lesions. Any pathological lymph nodes must be < 10 mm in the short axis.
- Immune-related Partial Response (irPR): At least a 30% decrease in the total tumor burden, including target lesions and new lesions, taking as a reference, the baseline sum of the diameters (e.g. percent change from baseline).

- Immune-related Stable Disease (irSD): Neither sufficient shrinkage to qualify for PR nor sufficient increase to qualify for progressive disease.
- Immune-related Progressive Disease (irPD): At least a 20% increase in the tumor burden (defined as the sum of diameters of target lesions and new lesions), taking as a reference, the smallest sum of diameters recorded since the treatment started (e.g. percent change from nadir, where nadir is defined as the smallest sum of diameters recorded since treatment start). In addition, the sum must have an absolute increase from nadir of 5mm.
- Not Applicable (NA): No target lesions at baseline.
- Not Evaluable (NE): Cannot be classified by one of the five preceding definitions.

NOTE:

- If lymph nodes are documented as target lesions the short axis is added into the sum of the diameters (e.g. sum of diameters is the sum of the longest diameters for non-nodal lesions and the short axis for nodal lesions). When lymph nodes decrease to non-pathological size (short axis <10mm) they should still have a measurement reported in order not to overstate progression.
- If at a given assessment time point all target lesions identified at baseline are not assessed, sum of the diameters cannot be calculated for purposes of assessing CR, PR, or SD, or for use as the nadir for future assessments. However, the sum of the diameters of the assessed lesions and the percent change from nadir should be calculated to ensure that progression has not been documented. If an assessment of PD cannot be made, the response assessment should be NE.
- All lesions (nodal and non-nodal) should have their measurements recorded even when very small (e.g., 2 mm). If lesions are present but too small to measure, 5 mm should be recorded and should contribute to the sum of the diameters, unless it is likely that the lesion has disappeared in which case 0 mm should be reported.
- If a lesion disappears and reappears at a subsequent time point it should continue to be measured. The response at the time when the lesion reappears will depend upon the status of the other lesions. For example, if the disease had reached a irCR status then irPD would be documented at the time of reappearance. However, if the response status was irPR or irSD, the diameter of the reappearing lesion should be added to the remaining diameters and response determined based on percent change from baseline and percent change from nadir.

7.1.3.3.3 Non-Target Lesions

Non-target lesions are not incorporated into tumor burden calculations. However, for the diagnosis of CR to be achieved, all non-target lesions must also resolve.

NOTE:

- In the presence of measurable disease, progression on the basis of solely non-target disease requires substantial worsening such that even in the presence of SD or PR in target disease, the overall tumor burden has increased sufficiently to merit discontinuation of therapy.
- Sites of non-target lesions, which are not assessed at a particular time point based on the assessment schedule, should be excluded from the response determination (e.g. non-target response does not have to be "Not Evaluable").

7.1.3.3.4 New Lesions

New lesions do not automatically qualify as irPD. The diameter of new lesions should be added to the sum of target lesions to assess disease burden.

Any equivocal new lesions should continue to be followed. Treatment can continue at the discretion of the investigator until the next scheduled assessment. If at the next assessment the new lesion is considered to be unequivocal, it should be added to the disease burden.

Table 8 presents the overall response at an individual time point for all possible combinations of tumor responses in target and non-target lesions with or without the appearance of new lesions for subjects with measurable disease at baseline.

7.1.3.3.5 Evaluation of Overall Response

Table 8 Evaluation of Overall Response for Subjects with Measurable Disease at Baseline

Overall Response	irRECIST (total tumor burden = target lesions + new lesions)	Non-target lesions	New lesions
irCR	Disappearance of all lesions	Absence	Absence
irPR	≥ 30% decrease in tumor burden compared with baseline	Any	Any
irSD	<30% decrease to < 20% increase in total tumor burden compared with baseline	Any	Any
irPD	≥ 20% increase in tumor burden compared with nadir or baseline with confirmation of progression by a second scan at least 4 weeks later	Any	Any

ir=immune related, CR=complete response, PR = partial response, SD=stable disease, PD=progressive disease, NA= Not applicable, and NE=Not Evaluable

NOTE:

- Subjects with a global deterioration of health status requiring discontinuation of treatment without objective evidence of disease progression at that time should be classified as having "symptomatic deterioration." Objective response status is determined by evaluations of disease burden. Every effort should be made to document the objective progression even after discontinuation of treatment.
- In some circumstances, it may be difficult to distinguish residual disease from normal tissue. When the evaluation of CR depends on this determination, it is recommended that the residual lesion be investigated (fine needle aspirate/biopsy) to confirm the CR.
- If patients experience irPD and remain clinically stable or improved, an exception may be granted to continue on study after discussion with the PI. If confirmed irPD is documented and an exception is granted, repeat imaging should be performed in 4-6 weeks and if further progression is documented then study treatment should be discontinued. If an isolated lesions progresses and is treated with local therapy (surgical resection or radiation therapy), imaging should be performed to document local stability and overall irRECIST re-evaluation.

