5.10 Clinical Criteria for Early Trial Termination

Early trial termination will be the result of the criteria specified below:

1. Quality or quantity of data recording is inaccurate or incomplete
2. Poor adherence to protocol and regulatory requirements
3. Incidence or severity of adverse drug reaction in this or other studies indicates a potential health hazard to subjects
4. Plans to modify or discontinue the development of the study drug
5. Lack of efficacy as defined by no responses in the first 10 patients AND <2 patients with stable disease at 24 weeks.

In the event of Merck decision to no longer supply study drug, ample notification will be provided so that appropriate adjustments to subject treatment can be made.

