7.1.3 Tumor Imaging and Assessment of Disease

The Immune Related RECIST (irRECIST) will be used for assessment of tumor response for the purposes of managing patients on protocol treatment and decision making for discontinuation of study therapy due to disease progression. These disease assessments will be performed by the investigator with site radiology reading. At least one measurable lesion according to RECIST 1.1 criteria must be present on a bi-dimensional imaging study (CT or MRI) at baseline. A measurable lesion is defined as measuring at least 10 mm in longest diameter or twice the slice thickness whichever is greater; the exception being that lymph nodes must measure 15 mm in short axis for lymph nodes.

The irRECIST criteria are described in Section 7.1.3.3. For the purposes of the efficacy endpoints of the study, response assessment based on irRECIST will be applied as the primary measure.

If imaging shows a complete response (CR) or partial response (PR), tumor imaging should be repeated at least 4 weeks later to confirm response, per irRECIST recommendations. Patients will then return to regular scheduled imaging, starting with the next scheduled imaging time point. Patients who obtain a confirmation scan do not need to undergo scheduled imaging assessment 2 weeks later (e.g. If a patient obtains a scan at Week 16 to confirm a Week 12 response, they will not also be required to complete the scheduled Week 18 scan).

If imaging shows PD, it is at the discretion of the investigator to keep a patient on study treatment or to stop study treatment until imaging is repeated approximately 4 weeks later in order to confirm PD, as described in the irRECIST recommendations. Patients that are deemed clinically unstable or who have biopsy proven new metastatic lesions are not required to have repeat imaging for confirmation. This decision will be based on clinical judgment of a patient's overall clinical condition, including performance status, clinical symptoms, and laboratory data. At a minimum, patients must meet the following criteria for continued treatment on study after disease progression is identified at a tumor assessment:

- Absence of symptoms and signs (including worsening of laboratory values) indicating disease progression
- No decline in ECOG performance status
- Absence of rapid progression of disease or of progressive tumor at critical anatomical sites (e.g., cord compression) requiring urgent alternative medical intervention.

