9.0 STATISTICAL ANALYSIS PLAN

9.1 Statistical Analysis Plan Summary

The primary objective is to determine whether pembrolizumab is an effective therapy in uveal melanoma. The null hypothesis is that the objective response rate (ORR; percentage of patients achieving a confirmed CR or PR) is not attractive (defined as $\leq 5\%$). The alternative hypothesis is that the response rate is of interest for further development (defined as $\geq 20\%$).

Product: MK-3475
Protocol/Amendment No. 03

The final analysis of the overall response rate will be performed with a power of 80% with one sided $\alpha=0.05$. It is calculated that at least 4 responses are needed out of a total of 29 patients to reject the null hypothesis.

To allow early termination of the trial due to lack of efficacy, the trial will be conducted in two stages per Simon's Optimal Design. If no responses are demonstrated in the first 10 patients, then the trial will be terminated early for futility. If ≥ 1 responses are observed, enrollment will continue to 29 patients. Notably, in the absence of ≥ 1 response, if ≥ 2 patients experience stable disease (SD) for >24 weeks, then the study may proceed to stage 2 if the sponsor and PIs are in agreement. This provision was added since the probability of early termination was as high as 10% even with a response rate of 20%.

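### Section 7.1.3.3.2 and Table 8 define irSD and irPD differently: some confirmed rises fit two Table 8 rows, and a few small ones get opposite labels

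*Combined protocol and SAP*

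**What the plan says.** Section 7.1.3.3.2 (Target Lesions) measures progression on the sum of target and new lesions. irPD needs a rise of at least 20% over the smallest sum since treatment start, and: "In addition, the sum must have an absolute increase from nadir of 5mm". irSD is the remainder: "Neither sufficient shrinkage to qualify for PR nor sufficient increase to qualify for progressive disease".

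Table 8 (Section 7.1.3.3.5) uses the same total burden, and Section 7.1.3.3.4 introduces it as giving the overall response at each time point. Its irSD row runs from less than a 30% "decrease to < 20% increase in total tumor burden compared with baseline". Its irPD row is a 20% or greater "increase in tumor burden compared with nadir or baseline with confirmation of progression by a second scan at least 4 weeks later". It carries no 5 mm condition and does not say which row wins when two apply. The note in Section 7.1.3.3.2 on a reappearing lesion has "response determined based on percent change from baseline and percent change from nadir", but it covers only that situation and does not rank the two.

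On use, Section 7.1.3 states: "For the purposes of the efficacy endpoints of the study, response assessment based on irRECIST will be applied as the primary measure". The same assessment guides treatment decisions. For stage 1, Section 9.1 says that, absent a response, if two or more "patients experience stable disease (SD) for >24 weeks, then the study may proceed to stage 2", subject to sponsor and PI agreement; Section 2.2.1 says the same. Sections 9.2.1 and 9.2.2.1 give this route without that proviso. Section 5.10 makes it a stopping rule: no responses and fewer than two "patients with stable disease at 24 weeks". Section 9.2.2.2.1 bases the main PFS on RECIST 1.1 and adds an investigator-assessed PFS by irRC.

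**The concern.** Each time point should have one label. Here the remainder definition in Section 7.1.3.3.2 ties the upper limit of irSD to nadir, while Table 8 ties it to baseline. The two limits part once a tumor has shrunk and regrown. The missing 5 mm condition matters separately when the sums are small.

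At stake is a count with a threshold of two patients, which can keep the trial open after a stage 1 with no responses, and the event dates in the irRC-based PFS. The trial is open-label and response is assessed by the investigator, so the label should not be left to be chosen after a borderline patient has been seen.

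**Working it through.** **1. The plan's own figures.** Inputs from Sections 9.1 and 9.2.1: 10 then 19 patients, at least 1 response to continue, at least 4 of 29 to reject, ORR 5% versus 20%.

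- Early termination = (1 − p)^10: 0.95^10 = 0.5987 and 0.80^10 = 0.1074 (Table 11: 0.599, 0.107).
- Rejection = Σ over x = 1 to 10 of P(X1 = x; n = 10, p) × P(X2 ≥ 4 − x; n = 19, p): 0.0468 at 5% and 0.8011 at 20% (Table 11: 0.047, 0.801).

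Table 11 reproduces.

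**2. The two rule sets.** B is the baseline sum, N the nadir and S the current sum, with the rise confirmed. I read the 5 mm as a minimum and let baseline count as nadir when it is the smallest sum.

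| | Section 7.1.3.3.2 | Table 8 |
|---|---|---|
| irPD | S ≥ 1.2N and S − N ≥ 5 mm | S ≥ 1.2N or S ≥ 1.2B |
| irSD | neither PR nor PD | 0.7B < S < 1.2B |

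**3. Mismatch 1: two Table 8 rows fit.** Illustrative sums in mm: baseline 100, then 75 (week 12), 95 (week 18), 95 (week 24).

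- Against baseline: 95/100 − 1 = −5%, so the irSD row is met.
- Against nadir: 95/75 − 1 = +26.7% and 95 − 75 = +20 mm, confirmed six weeks later, so the irPD row is also met.
- Section 7.1.3.3.2: irPD only.

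The Table 8 overlap runs from the larger of 1.2N and just above 0.7B up to just below 1.2B. With B = 100:

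- N = 90: 108 to <120
- N = 75: 90 to <120
- N = 60: 72 to <120
- N ≤ 70/1.2 = 58.3: >70 to <120

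A rise to 120 or more (for example 100, 75, 125) is irPD only in both texts.

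**4. Mismatch 2: opposite labels.** Baseline and nadir 20, then 24.5, confirmed.

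- 24.5/20 − 1 = +22.5%, so Table 8 gives irPD.
- 24.5 − 20 = 4.5 mm, under 5 mm, so Section 7.1.3.3.2 gives irSD.

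This needs 0.2N < 5, so N < 25 mm. The band is 24 to <25 at N = 20, 12 to <15 at N = 10, and empty from 25 mm up. Sums this small are possible: one measurable lesion suffices (Section 7.1.3.2) and the minimum size is 10 mm (Section 7.1.3.1).

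**5. Outer bound on the design.** If the SD route always opened stage 2, rejection would be P(X ≥ 4; n = 29, p): 0.0548 at 5% and 0.8596 at 20%. The differences are 0.0548 − 0.0468 = 0.0080 and 0.8596 − 0.8011 = 0.0585. They belong to the whole SD route. Relabelling the occasional patient can produce only a fraction of them.

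**The case against.** The best reply is that mismatch 1 is an overlap and not a contradiction. Table 8's irPD row already includes nadir, so 100, 75, 95, 95 is irPD in both texts, and reading Table 8 with the remainder definition removes the irSD label. That stands. A reader might infer that such patients receive opposite labels and that the stage-1 answer must differ, but this happens only if someone applies the irSD row and ignores Section 7.1.3.3.2. What remains is that Table 8 states no precedence. The reply also does nothing for mismatch 2.

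Mismatch 2 is narrow, and that stands too.

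Because two SD patients suffice, a reader might treat one disputed label as likely to decide the gate. Given no responses and exactly one disputed patient, the chance is 9q(1 − q)^8, where q is the assumed chance of 24-week SD in each of the other nine: 0.39, 0.30 and 0.18 at q = 0.10, 0.20 and 0.28 (0.28 being the 23-week SD figure in Section 4.2.1 for ipilimumab). These figures presuppose the disputed patient, whose probability the documents do not give, so they do not measure the problem. Under Sections 2.2.1 and 9.1 the SD count also only creates an option that needs agreement.

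Lastly, the SD rule names no response criteria. Its link to irRECIST rests on Section 7.1.3. The RECIST 1.1 appendix cannot be read in the public copy, so a different SD definition for the gate cannot be excluded.

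**Conclusion.** The inconsistency is real and worth correcting, but its reach is small. On one tumor burden, the two texts leave some confirmed rises with two Table 8 rows against one label in Section 7.1.3.3.2. They give opposite labels only for confirmed rises of at least 20% but under 5 mm, from nadir sums below 25 mm.

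The exposed outputs are the 24-week SD count, if irRECIST governs it, and the supplementary irRC-based PFS, if irRC there means the criteria of Section 7.1.3.3, which carries that name in its heading. Table 11 and the RECIST 1.1 PFS are not affected. The irPR threshold, at least 30% below baseline, is the same in both texts.

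A reader might infer inflated type I error or bias in a known direction. The documents support neither: the frequency of such patients is unknown, and the outer limits for the entire SD route are 0.055 and 0.860. An effect on response duration cannot be established either, since Section 9.2.2.2.3 names no end event.

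**What to change.** For endpoint derivation and the stage-1 SD count, restate Table 8's irSD row as neither irPR nor irPD, so that a time point meeting irPD is not counted as SD. Cross-refer to it from Section 9.2.2.

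Limit this to the irSD/irPD overlap. A general line giving confirmed irPD precedence would also catch scans meeting both irPR and irPD. In 100, 40, 50, 50, the sum of 50 is −50% from baseline and +25% and +10 mm from nadir. Such a line could cancel the confirmation of a response and so change the primary ORR.

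The 5 mm condition and the nadir or baseline reference need a separate step. Sections 7.1.3.3.2 and 7.1.3.3.5 must be reconciled with each other and with Section 7.1.3, so that one irPD definition applies. Because confirmed progression also ends treatment (Sections 5.2.3 and 5.8), which definition governs treatment is left to the sponsor and investigators. Until this step is taken, mismatch 2 remains open.

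The cost is one restated table row, a cross-reference, and agreement on one irPD wording. No new data or visits are needed.

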5.2.3 Duration of Therapy

Pembrolizumab will be administered every 3 weeks until one of the following occurs:

- Confirmed radiographic disease progression

Protocol date: August 30, 2016

Confidential

- Indications for subject discontinuation from the trial as outlined in section 5.8
- Treatment for 24 months
- Confirmed complete response (CR)

In the event of a confirmed complete response (CR), it is at the discretion of the investigator to keep a patient on study treatment or to suspend study treatment based on the criteria.

- Radiographic CR as defined by RECIST criteria
- Confirmation with repeat imaging at least 4 weeks after the initial imaging

Patients will continue to be monitored with scheduled disease assessments as described in the protocol (as if the patient were continuing on study treatment), and in the event of a disease recurrence, pembrolizumab may be resumed (Second Course treatment) upon disease recurrence in these patients. Second Course treatment with pembrolizumab may be given for up to 12 additional months.

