5.8 Subject Withdrawal/Discontinuation Criteria

Subjects may withdraw consent at any time for any reason or be dropped from the trial at the discretion of the investigator should any untoward effect occur. In addition, a subject may be withdrawn by the investigator or the Sponsor if enrollment into the trial is inappropriate, the trial plan is violated, or for administrative and/or other safety reasons. Specific details regarding discontinuation or withdrawal are provided in Section 7.1.4 – Other Procedures.

A subject must be discontinued from the trial for any of the following reasons:

- The subject or legal representative (such as a parent or legal guardian) withdraws consent.
- Confirmed radiographic disease progression

Note: For unconfirmed radiographic disease progression in the absence of clinical deterioration, patients may continue on study.

- Unacceptable adverse experiences as described in Section 5.2.1.2
- Intercurrent illness that prevents further administration of treatment
- Investigator's decision to withdraw the subject
- The subject has a confirmed positive serum pregnancy test
- Noncompliance with trial treatment or procedure requirements
- The subject is lost to follow-up
- Completed 24 months of treatment with pembrolizumab

Note: 24 months of study medication is calculated from the date of first dose. Subjects who stop pembrolizumab after 24 months may be eligible for up to one year of additional study treatment if they progress after stopping study treatment provided they meet the requirements detailed in Section 7.1.2.6.

- Administrative reasons

The End of Treatment and Follow-up visit procedures are listed in Section 6 (Protocol Flow Chart) and Section 7.1.5 (Visit Requirements). After the end of treatment, each subject will be followed for 30 days for adverse event monitoring (serious adverse events will be collected for 90 days after the end of treatment as described in Section 7.2.3.1). Subjects who discontinue for reasons other than progressive disease will have post-treatment follow-up for disease status until disease progression, initiating a non-study cancer treatment, withdrawing consent or becoming lost to follow-up. After documented disease progression

each subject will be followed by telephone for overall survival until death, withdrawal of consent, or the end of the study, whichever occurs first.

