If repeat imaging shows an objective response or stable disease relative to baseline, treatment with pembrolizumab will continue/resume and the next imaging studies will be conducted every 6 weeks as previously scheduled. If repeat imaging confirms PD, patients will be discontinued from study therapy.

In patients who discontinue study therapy early without documented disease progression, every effort should be made to continue monitoring their disease status by radiologic imaging following the guidelines described in Section 7.1.6.4.

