7.1.6.4.1 Survival Follow-up

Once a subject experiences confirmed disease progression or starts a new anti-cancer therapy, the subject moves into the survival follow-up phase and should be contacted by telephone every 12 weeks to assess for survival status until death, withdrawal of consent, or the end of the study, whichever occurs first.

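### Sections 5.2.3, 5.8 and 7.1.3 end pembrolizumab at confirmed progression, but the note to Table 8 in 7.1.3.3.5 lets it continue by exception, and none of the three refers to that exception

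*Combined protocol and SAP*

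**What the plan says.** **Sections that stop treatment.**

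- Section 5.2.3 introduces its list of stopping events with "Pembrolizumab will be administered every 3 weeks until one of the following occurs", and the first item is "Confirmed radiographic disease progression".
- Section 5.8 opens its list with "A subject must be discontinued from the trial for any of the following reasons", and confirmed radiographic progression is on it. The note attached to that item reads "For unconfirmed radiographic disease progression in the absence of clinical deterioration, patients may continue on study".
- Section 7.1.3 states: "If repeat imaging confirms PD, patients will be discontinued from study therapy".

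**Section that lets treatment continue.** A note to Table 8 in 7.1.3.3.5 says that for patients with irPD whose clinical condition is stable or better, "an exception may be granted to continue on study after discussion with the PI". It goes on: "If confirmed irPD is documented and an exception is granted, repeat imaging should be performed in 4-6 weeks". The same sentence ends study treatment if that scan shows further progression.

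**Survival follow-up.** Section 7.1.6.4.1 says "Once a subject experiences confirmed disease progression or starts a new anti-cancer therapy, the subject moves into the survival follow-up phase", with telephone contact every 12 weeks. Section 1.2 uses the same trigger, and 5.8 also places telephone follow-up after documented progression. Footnote 18 to the flow chart in 6.1 instead ties telephone follow-up to stopping therapy because of progression.

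**The concern.** For a patient with confirmed irPD who is clinically stable and has been granted an exception, no site can follow all four treatment passages. Stopping satisfies 5.2.3, 5.8 and 7.1.3; continuing satisfies 7.1.3.3.5 but breaches the mandatory wording of 5.8. It is then unclear whether such dosing should be logged as a protocol deviation.

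Three centres take part (2.2.1). If they read the text differently, time on drug, the period over which adverse events are collected, and the primary reason for discontinuation tabulated under 9.2.4 will depend partly on which section a centre followed. The exception is also incompletely specified: its end point, further progression, is not tied to any reference measurement.

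**Working it through.** The point rests on the text, and the plan gives no figure for it. The passages side by side:

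| Section | Trigger | Consequence | Refers to the exception? |
|---|---|---|---|
| 5.2.3 | Confirmed radiographic progression | Dosing ends | No |
| 5.8 | Confirmed radiographic progression | Mandatory discontinuation; relaxation for unconfirmed progression only | No |
| 7.1.3 | Progression confirmed on repeat imaging | Study therapy ends | No |
| 7.1.3.3.5, note to Table 8 | Confirmed irPD, clinically stable, PI consulted | Treatment may continue; scan at 4-6 weeks; stop on further progression | It is the exception |

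**Can the text be read so that it agrees?** Three readings were tried.

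1. *The exception covers only unconfirmed irPD.* It does not. The sentence names confirmed irPD, and the irPD row of Table 8 already requires a confirming second scan.
2. *Remaining on study means follow-up without drug.* It does not. The same sentence says when study treatment is to stop, so treatment must be continuing.
3. *The note is a specific carve-out from a general rule.* This is plausible as intent. But 5.8 is mandatory, its own note draws the line at unconfirmed progression, and no stopping section points to 7.1.3.3.5.

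**Reference for further progression.** Section 7.1.3.3.2 measures irPD from the nadir, and Table 8 from nadir or baseline. The note does not say whether further progression is measured from baseline, nadir or the confirming scan.

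**Length of the exception before its scan.** At one infusion every 3 weeks, 4/3 = 1.3 and 6/3 = 2, so roughly one to two dosing intervals pass before the required scan.

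**Follow-up trigger.** Under 7.1.6.4.1 and 1.2 the trigger is confirmed progression; under footnote 18 it is stopping therapy for progression. For a patient who stops at confirmed progression the two coincide. They differ only for a patient still being treated under the exception.

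**Does it reach the main analyses?**

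- *Table 11.* With response rate p, early termination is (1-p)^10. Rejection is the sum over x = 1 to 10 of P(X1 = x) × P(X2 ≥ max(0, 4-x)), where X1 is binomial(10, p) and X2 is binomial(19, p). At p = 0.05 this gives 0.5987 and 0.0468 (stated 0.599 and 0.047). At p = 0.20 it gives 0.1074 and 0.8011 (stated 0.107 and 0.801). No stopping rule for the drug enters these figures.
- *PFS (9.2.2.2.1).* Progression is dated at the first assessment documenting RECIST 1.1 progression, whether or not the drug has been stopped.
- *OS (9.2.2.2.2).* This runs from first dose to death, so the date of entry to survival follow-up does not alter it.
- *Adverse events and reason for discontinuation (9.2.3, 9.2.4).* These are descriptive, and they are where a difference would show.

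**The case against.** The best defence is that the note calls itself an exception and requires discussion with the PI. An exception presupposes a general rule, so the likely defect is a missing cross-reference, and the PI's involvement limits divergence between centres. That is fair as to intent. It does not settle the text, because 5.8 is mandatory and sets its own boundary at unconfirmed progression.

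On follow-up, the defence is stronger. The flow chart places survival follow-up under post-treatment, footnote 18 requires that therapy has stopped, 7.1.6.4 opens with subjects who have discontinued treatment, and the sentence in 1.2 sits in a paragraph about such patients. Read in context, these passages mostly concern patients already off drug. What remains is that 7.1.6.4.1 and 1.2 name confirmed progression itself as the trigger, which makes this a secondary inconsistency.

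It can also be said that the minimum conditions in 7.1.3 for continued treatment after progression already govern the exception. Their wording could extend that far, but they stand in a paragraph about awaiting the confirming scan, and 7.1.3.3.5 neither repeats nor cites them. The documents leave this open.

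A reader might further infer that a patient treated under the exception is dosed without monitoring. The documents do not support that. Flow-chart procedures precede each dose (5.2.2), as do vital signs (7.1.2.3), review of laboratory results (7.1.4.1) and assessment for events of clinical interest (7.2.3.2). Treatment visits every 3 weeks include examination and laboratory tests (7.1.6.2.1), and the note itself requires a scan.

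**Conclusion.** The contradiction stands: 5.2.3, 5.8 and 7.1.3 end pembrolizumab at confirmed progression, and 7.1.3.3.5 allows it to continue without any of them acknowledging this. The conflict over the survival follow-up trigger is real but secondary.

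The size is limited. Only patients granted an exception are affected, and the documents give no basis for estimating how many. The items affected are time on drug, adverse event exposure and reason for discontinuation.

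Three stronger inferences are not supported:

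- That every clinically stable patient with confirmed irPD is affected. An exception must first be granted.
- That treatment under the exception is open-ended. The 24-month limit and the other discontinuation criteria in 5.8 still apply.
- That the efficacy results are compromised. Table 11, PFS and OS do not depend on when the drug stops. The plan does not say whether a response first seen under the exception would count toward the four required, but nothing in the documents shows an effect on ORR, and none is claimed.

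The conclusion assumes only that the current wording of each section is in force. It takes no position on whether treatment should continue after confirmed progression.

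**What to change.** Reconcile 5.2.3, 5.8, 7.1.3 and 7.1.3.3.5 so that one rule governs dosing after confirmed irPD. Which rule is for the sponsor to decide. The text can be made consistent either by cross-referring to the exception in 5.2.3, 5.8 and 7.1.3, or by removing it from the note to Table 8.

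Align the survival follow-up trigger in 1.2, 5.8, 7.1.6.4.1 and flow-chart footnote 18 with that choice.

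If the exception is kept, also state:

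- the reference sum against which further progression is judged;
- whether the continuation conditions in 7.1.3 apply to a patient treated under it.

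The cost is amendment wording in these sections. No patients or procedures are added, and the sample size is unchanged.
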